Table 2. Detail of Blood Draws for Monitoring Safety and Compliance and Secondary Endpoint Serum Biochemical Parameters
Teriparatide

Treatment Group Base-line Bi-weekly visits until steady state Q1 Visit Q2 Visit Q3 Visit 1 Year 15 mo 18mo 21mo 2 yr
or Safety: Serum Calcium & PTH X X X X X X X X X X X X

For Compliance: BSAP X X X X X X X X X X

Secondary Endpoints: FGF23, P1NP, Sclerostin, DKK-1 & PTH Ratio X X X X X

Alendronate

Treatment Group Base-line Monthly visits until steady state Q1 Visit Q2 Visit Q3 Visit 1 Year 15 mo 18mo 21mo 2yr

For Safety and Compliance: BSAP X X X X X X X X X X

Secondary Endpoints: Serum Calcium, PTH & PTH Ratio, FGF23, P1NP, Sclerostin, DKK-1 X X X X X

Standard of Care Controls Base-line Q2 Visit 1 Year 15mo 18mo 21mo 2 yr

Secondary Endpoints: All of the above Serum Biochemical Parameters X X X X X

Cinacalcet will be adjusted in 30 mg steps up to a maximum daily dose of 180 mg if needed to keep intact PTH at levels less than 200 pg/mL. If by six weeks, this fails to achieve PTH levels less than 200 pg/mL, patients will be excluded from further study participation. In the rare case where PTH level maintenance requires cinacalcet doses that induce serum calcium levels below 8.5 mg/dL, treatment will cease for two weeks after which calcium will be re-measured. At two weeks if calcium remains below 8.5 mg/dL, patients will be excluded from further participation in the study. If calcium is normalized, cinacalcet will be reinstated at half of the prior dose. Calcium will be checked again at the next monitoring visit. If at any measurement point PTH levels are less than 60 pg/mL cinacalcet will be withheld and reinstated if levels are again above 200 pg/mL.

Treatment Protocol for Alendronate: Patients with normal or high bone turnover will receive a starting dose of 35 mg alendronate p.o. once per week. Patients will be carefully instructed to follow the manufacturer's recommendations for administration. Serum calcium will be rechecked 1 week +/- 3 days after starting therapy. Dosage will be adjusted according to changes in the bone turnover marker

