BSAP from blood drawn at monthly monitoring visits for the first 3 months, thereafter at quarterly monitoring visits. BSAP is expected to go down, but to avoid over-suppression, will not be allowed to go below the low normal range of the assay, as is done clinically. Our data show that mid/normal ranges of these markers in CKD-5D patients indicate low turnover^{48, 49} If this safety threshold is crossed, treatment will be stopped until values are back above the threshold at a regularly scheduled monitoring visit. Once demonstrably back within safety threshold, treatment will be reinstated at half of the initial dose (35 mgs every other week). If BSAP does not go down at least 8% over a one month period, treatment doses will be doubled to 70 mgs per week. If they still remain high, study coordinators will carefully review with the patients the mode of drug intake and possible compliance lapses.

Primary Endpoint At one year after baseline, we will assess bone mass using QCT BMD measurements of the total hip and compare 1 and 2 year changes in bone mass between the treatment and control groups. Total hip will be used as the primary endpoint site because in our prior funding period we showed that changes at the total hip in QCT BMD are more pronounced than at the spine⁶. The Secondary endpoint will be differences between the treatment and control groups in changes in coronary artery calcifications by MDCT. This will be relevant regardless of bone effects.

Other secondary endpoints tracked at baseline, 6 months, and 1 year, 18 and 24 months will include serum biochemical markers of bone activity; FGF 23, BSAP, TRAP5b, P1NP, Sclerostin, and DKK1.

Additionally we will record 1) Change in QCT BMD of the spine to compare with the hip) 2) Changes in DXA BMD of the hip and spine (to determine whether the more commonly available DXA results are equivalent to QCT and 3) Changes in aortic and heart valve calcification (to compare with the coronary artery calcifications).^{50,51} 4) Whole body composition (%fat vs %lean) as it relates to survival in CKD-5D patients.

Attachments

Attach Type	File Name
ResearchProcedures	figure 3 7.22.2019 pdf.pdf

Data Collection: List the data or attach a list of the data to be collected about or from each subject (e.g. interview script, survey tool, data collection form for existing data).

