Both teriparatide and alendronate have been used in low bone densityosteoporotic patients for more than 11 and 15 years, respectively. In the experience of the PI they are generally well-tolerated. The PI has used these medications in his osteoporosis practice in patients with and without CKD for over 10 years and has experience in long-term monitoring of these treatments. Alendronate is indicated for the treatment of low bone densityosteoporosis in postmenopausal women and for treatment to increase bone mass in men with bone lossosteoporosis. Alendronate is contraindicated in patients with the following conditions: abnormalities of the esophagus which delay esophageal emptying such as stricture or achalasia; inability to stand or sit upright for at least 30 minutes; hypocalcemia, that is, blood calcium levels below normal range for the employed assay; prior hypersensitivity to alendronate. Use of alendronate in CKD-5D patients is not specifically mentioned as a contraindication in the package inserts or on the safety web page. However, it is recommended to not give alendronate to patients with GFR < 35 mL/min. A post-hoc data analysis of 581 women with reduced renal function (GFR < 45 mL/min.) who were participating in the fracture intervention trial showed that alendronate was safe and effective.⁶⁰

The major observed side effects for alendronate are gastrointestinal complaints which include abdominal pain, nausea, dyspepsia, constipation, diarrhea, and flatulence. Regurgitation, esophageal ulcer, vomiting, dysphagia, abdominal distention, and gastritis have occurred at a lower frequency. Rarely, taste perversion has been reported. The combination of alendronate and naproxen has been reported as synergistic for development of gastric ulcers. The frequency of adverse effects increases with higher dosages. Adverse effects usually have been mild when patients adhered to prescribing instructions. In a 12-week multicenter, randomized, double-blind, placebo-controlled study of 450 post-menopausal women, the incidence of gastrointestinal side effects was comparable (13% vs. 11%) in the treatment and placebo groups.⁶¹

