Metabolic side effects have included reductions in serum calcium and phosphorus levels as a result of the inhibition of bone resorption. These reductions generally have been mild, asymptomatic, and transient. Musculoskeletal side effects have included bone, muscle or joint pain in approximately 4% of patients. Localized osteonecrosis of the jaw generally associated with tooth extraction and/or local infection has been reported rarely and is likely associated with over-suppression of bone turnover. Also, low-energy femoral shaft and sub-trochanteric insufficiency fractures have been reported in post-marketing experience after long-term use of alendronate (>5 years). Again, over-suppression of turnover is a likely cause.

Teriparatide is indicated: a) for the treatment of postmenopausal women with low bone densityosteoporosis at high risk for fracture, b) to increase bone mass in men with primary or hypogonadal low bone densityosteoporosis at high risk for fracture, and c) for the treatment of men and women with bone lossosteoporosis associated with sustained, systemic glucocorticoid therapy (daily dosage equivalent to 5 mg or greater of prednisone) at high risk for fracture. The risks associated with using teriparatide for treatment of osteoporosis in men and women was assessed in two randomized double blind placebo controlled trials of 1,382 patients, mean age 67 years.⁷¹ All-cause mortality, incidence of serious adverse events and discontinuation due to adverse events, were similar or even lower in the teriparatide group. Adverse reactions that were higher in the teriparatide group include: arthralgia, pain, and nausea. Other adverse reactions include dizziness, leg cramps, and injection site reactions. Persistent hypercalcemia is a rare occurrence in these patients. Teriparatide is not used in patients with hypercalcemic disorders and Paget's disease; these are inclusion/exclusion criteria for this study.

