Teriparatide for patients with low bone turnover: Patients with increased baseline risk of osteosarcoma will be excluded from this study (Paget's disease of bone, pediatric populations and young adults with open epiphyses, or prior external beam or implant radiation therapy). Our inclusion/exclusion criteria eliminate all of these patients. There are no direct contraindications given for CKD patients given in the package inserts and the safety web page. However, because bone loss with CKD-5D is not specifically addressed in the indications, we have obtained an IND (Investigational New Drug) from the FDA.

If during the monthly monitoring calls/visits or quarterly visits patients complain of new onset adverse reactions such as arthralgia, pain, nausea, dizziness or leg cramps, the patients will be counseled regarding standard treatment measures. Follow-up contact will be made in one week and if symptoms persist, treatment will be discontinued until the next regularly scheduled quarterly monitoring visit. Follow-up communication will occur within 1 week +/- 3 days and if problems persist despite discontinuation, patients will be referred to his/her primary care provider.

If patients complain of injection site reactions, they will be counseled regarding their injection technique and follow-up contact will be made in one week +/- 3 days. If reactions persist, treatment will be discontinued until next regularly scheduled quarterly monitoring visit. If problems persist despite discontinuation, patients will be referred to his/her primary care provider and their participation in the study will end.

In the rare case where PTH level maintenance requires cinacalcet doses that induce serum calcium levels below 8.5 mg/dL, treatment will cease and patients will be excluded from further participation in the study.

Alendronate for patients with normal or high bone turnover: Our inclusion/exclusion criteria cover all of the above-mentioned contraindications. To be safe, we have obtained an IND from the FDA.

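### Alendronate is doubled to 70 mg weekly on BSAP alone, with no current calcium required, although the plan lists hypocalcaemia as a contraindication

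*Combined protocol and SAP*

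**What the plan says.** Research Procedures, Treatment Protocol for Alendronate, sets a start of 35 mg weekly. BSAP is drawn monthly for three months and quarterly after that, and it drives every written dose change. Treatment stops if BSAP falls below the low normal limit and restarts at half dose once BSAP recovers. The increase is governed by: "If BSAP does not go down at least 8% over a one month period, treatment doses will be doubled to 70 mgs per week".

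Calcium appears in this arm in three places:

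- **At entry.** Corrected calcium must be normal (Study Population, inclusion criteria).
- **Once early on treatment.** "Serum calcium will be rechecked 1 week +/- 3 days after starting therapy". No action is attached to the result.
- **In Table 2, as an endpoint.** The alendronate safety row reads "For Safety and Compliance: BSAP X X X X X X X X X X". Calcium sits in the row below: "Secondary Endpoints: Serum Calcium, PTH & PTH Ratio, FGF23, P1NP, Sclerostin, DKK-1 X X X X X".

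Among the contraindications to alendronate, Potential Risks lists "hypocalcemia, that is, blood calcium levels below normal range for the employed assay". It also names falls in calcium as a drug effect and adds: "These reductions generally have been mild, asymptomatic, and transient". Safety Precautions answers the contraindications with: "Our inclusion/exclusion criteria cover all of the above-mentioned contraindications".

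**The concern.** Eligibility criteria act once, before the first dose, whereas the drug can lower calcium afterwards. A criterion met at entry therefore cannot cover a contraindication that may develop on treatment. The week-1 check comes before any possible doubling and has no written consequence.

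Followed exactly, the rule doubles a calcium-lowering drug in a dialysis patient without asking for a current calcium. It would do so even in a patient who by then meets the plan's own contraindication.

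The plan treats low calcium as a real hazard elsewhere. It says cinacalcet may cause hypocalcaemia, and the exclusion criteria let patients enter while taking calcimimetics. For study cinacalcet in the other arm it writes a rule: if doses "induce serum calcium levels below 8.5 mg/dL, treatment will cease for two weeks after which calcium will be re-measured". It also passes over a third osteoporosis drug because severe hypocalcaemia leading to hospital admission has been reported. That is a different drug and says nothing about the rate with alendronate, but it shows that the hazard is recognised in this population.

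**Working it through.** The plan states no figure to reproduce. The check compares the dosing rules and then counts the time between scheduled calcium results and the visits where a doubling can occur.

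**Rules side by side**

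| | Teriparatide/cinacalcet arm | Alendronate arm |
|---|---|---|
| Analytes in Table 2 safety row | Calcium and PTH | BSAP |
| Calcium values with a dosing action | 8.5, 10.2 and 11.0 mg/dL | None |
| Symptom-based hold rules (Safety Precautions) | Yes | Yes: gastrointestinal symptoms and musculoskeletal pain |

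The missing calcium condition is in the prose, so it does not depend on how Table 2 is read.

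**Inputs for the timing**

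- Week-1 calcium: day 7 ± 3, so day 4 to day 10.
- Possible early doubling visits: months 1, 2 and 3.
- Conversion (assumed): 365.25/12 = 30.4 days per month; 30.4/7 = 4.35 weekly doses per month.

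**Age of the last explicitly scheduled calcium at doubling** = visit day − (10 to 4)

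- Month 1 (day 30.4): 20–26 days.
- Month 2 (day 60.9): 51–57 days.
- Month 3 (day 91.3): 81–87 days, unless calcium is drawn that day (see below).

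**Doses of 70 mg before the next scheduled calcium** = months to next draw × 4.35

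Two readings are possible. The calcium row in Table 2 has five marks, which fit baseline, 6, 12, 18 and 24 months, the times given in Study Design and for the secondary endpoints in Research Procedures. Alternatively, the quarterly safety bloods in Safety Precautions, whose analytes are not named, may include calcium.

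| Doubling at | Six-monthly reading (next draw month 6) | Quarterly reading (next draw month 3) |
|---|---|---|
| Month 1 | 5 × 4.35 = 21.7, about 22 | 2 × 4.35 = 8.7, about 9 |
| Month 2 | 4 × 4.35 = 17.4, about 17 | 1 × 4.35 = 4.35, about 4 |
| Month 3 | 3 × 4.35 = 13.05, about 13 | Same-day value |

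Table 2's column alignment is lost in the available text, and its mark counts are not fully reliable: the teriparatide calcium row shows 12 marks under 10 headings. The choice between the two readings therefore stays open. On either one, no calcium is explicitly scheduled between week 1 and a month-1 or month-2 doubling.

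**The case against.** Several points favour the plan.

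- **Other safeguards.** The investigator is a nephrologist who is available by phone and reviews adverse events. The team meets weekly, and calcium from medical records is collected. Low calcidiol is an exclusion, and the clinics check it twice a year and supplement. These lower the risk. But oversight needs a result to act on, record-based calcium has no stated frequency or link to dosing, and calcidiol monitoring is not calcium monitoring.
- **Who gets doubled.** The plan attributes the calcium fall to reduced bone resorption, and doubling is for patients whose marker has barely moved. They may be less likely to have had a drug-induced fall by then. That is a fair point about the moment of doubling, but it does not cover falls after the increase or falls from other causes such as a calcimimetic.
- **Schedule.** Objectives puts the serum secondary endpoints at quarterly visits. Its list does not name calcium, but Table 2 groups calcium with several of those endpoints. This supports the quarterly reading and the smaller dose counts. The larger counts should not be taken as established.
- **Mildness.** The plan describes the falls as generally mild and transient. That limits the likely harm without removing the stated contraindication.
- **Unseen attachments.** The study drug form, prescribing information, IND correspondence and attached figures were not available and could hold a calcium schedule. The finding is limited to the visible text for that reason.

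**Conclusion.** The concern holds. In the visible plan, alendronate is doubled on BSAP alone, no current calcium is required, and no calcium value changes an alendronate dose, although below-normal calcium is listed as a contraindication. The omission is clear from the prose.

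Its clinical size is unknown: the documents give neither a hypocalcaemia rate nor an expected number of doublings. What can be measured is the gap at a month-1 or month-2 doubling. The last explicitly scheduled calcium is three to eight weeks old, and between about 4 and 22 doses of 70 mg follow before the next, depending on the reading of Table 2 and the month of doubling.

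Confidence is medium because of the unseen attachments and the damaged table. The change is worth making because the rule bears on safety and the correction is cheap. Given the informal safeguards, the gap does not by itself make the arm unsafe.

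**What to change.** 1. Add serum calcium to the alendronate safety row of Table 2, run on blood already drawn for BSAP at the monthly and quarterly visits, and show the week-1 check in the table.
2. Require a current calcium within the normal range before doubling to 70 mg.
3. State that a below-normal calcium on treatment leads to a hold and recheck. The cinacalcet rule in Research Procedures is a pattern to adapt; the sponsor's clinicians should set the limits and the restart rule.

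**Cost.** After baseline, BSAP is drawn at months 1, 2, 3, 6, 9, 12, 15, 18, 21 and 24. If quarterly bloods already include calcium, the added assays are at months 1 and 2, so 2 per patient. On the six-monthly reading they are at months 1, 2, 3, 9, 15 and 21, so 6 per patient. No extra blood draws are needed. The amendment covers two rows of one table and one paragraph. The downside is a few delayed doses, some of them for mild falls that would have resolved unaided. If an attachment already holds such a rule, it should be repeated beside the doubling instruction.

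### The alendronate dose-increase sentence contradicts the restart dose after an over-suppression hold, and does not say what BSAP is compared with or how often the test applies

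*Combined protocol and SAP*

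**What the plan says.** All of this is in the combined protocol and SAP, Research Procedures, under Treatment Protocol for Alendronate and in Table 2.

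- Start: a "starting dose of 35 mg alendronate p.o. once per week".
- Lower limit: BSAP "will not be allowed to go below the low normal range of the assay". The stated purpose is to prevent turnover being suppressed too far.
- Hold: "If this safety threshold is crossed, treatment will be stopped until values are back above the threshold at a regularly scheduled monitoring visit".
- Restart: "treatment will be reinstated at half of the initial dose (35 mgs every other week").
- Increase, in the very next sentence: "If BSAP does not go down at least 8% over a one month period, treatment doses will be doubled to 70 mgs per week".
- After the increase: "If they still remain high, study coordinators will carefully review with the patients the mode of drug intake and possible compliance lapses".
- Timing in the text: dose is adjusted on "BSAP from blood drawn at monthly monitoring visits for the first 3 months, thereafter at quarterly monitoring visits".
- Timing in Table 2, alendronate block: "Monthly visits until steady state", then quarterly, with BSAP drawn out to two years.

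The increase sentence gives a window of one month. It does not say whether the change is measured from baseline, from the previous visit or from the value at restart. It does not say whether the test is made once or repeatedly, sets no condition on the level of BSAP, and neither includes nor excludes patients restarted after a hold.

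**The concern.** The increase sentence follows directly on the restart sentence, so a coordinator working down the paragraph could apply it to a patient who has just come back from a hold. For that patient its two halves give different doses. The paragraph itself adds that mid-normal marker values in CKD-5D indicate low turnover. A patient just back above the low-normal limit is therefore not, on the protocol's own data, one whose BSAP is high.

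Separately, a marker that responds and then levels off falls less each month. If the test is visit to visit and repeated, a good response can end by meeting the criterion for non-response.

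At stake is a stated rule that can work against the paragraph's own aim. Potential Risks names over-suppression as a likely factor in jaw osteonecrosis, reported rarely, and in femoral insufficiency fractures, reported after more than five years of use. Two people following the text could also give the same patient different doses.

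**Working it through.** **1. The plan's own figures.** Starting dose 35 mg per week. Doubled: 35 × 2 = 70 mg per week, as stated. Halved: 35 / 2 = 17.5 mg per week, which is 35 mg every other week, as stated. Both reproduce from the starting dose.

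**2. The same sentence for a restarted patient (17.5 mg per week).**

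- If the word *doubled* governs: 17.5 × 2 = 35 mg per week, a twofold rise.
- If the milligram figure governs: 70 / 17.5 = 4, a fourfold rise.

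The two instructions coincide only when the current dose is 35 mg weekly.

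**3. Can the case arise while draws are monthly?** Yes, but on the text's schedule it needs a particular sequence: below the limit at month 1, back above it and restarted at month 2, fall of less than 8% at month 3.

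**4. How often would a stable patient meet the trigger?** Inputs are the BSAP assay limits in the Serum Biochemical Parameters paragraph (intra-assay CV below 6%, inter-assay CV below 8%). I assume normal assay error at those limits and no biological variation. SD of a change = CV × √2.

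- CV 8%: SD = 11.3%. With no true change, P(observed fall < 8%) = Φ(8 / 11.3) ≈ 76%.
- CV 6%: SD = 8.5%. P = Φ(8 / 8.5) ≈ 83%.

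So a restarted patient whose BSAP is simply steady would usually meet the trigger, if the rule applies to that patient.

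**5. Effect of the comparison value.** The documents give no BSAP time course, so these paths are assumptions: BSAP(t) = 100 − P(1 − 0.5^(t/h)), where P is the eventual fall, h the half-time and t is in months. Dose is held fixed. With h = 1 month:

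| P | BSAP at months 0 to 3 | Change from previous visit | Change from baseline | First visit-to-visit trigger |
|---|---|---|---|---|
| 20 | 100, 90, 85, 82.5 | −10%, −5.6%, −2.9% | −10%, −15%, −17.5% | month 2 |
| 30 | 100, 85, 77.5, 73.8 | −15%, −8.8%, −4.8% | −15%, −22.5%, −26% | month 3 |
| 40 | 100, 80, 70, 65 | −20%, −12.5%, −7.1% | −20%, −30%, −35% | month 3 |
| 60 | 100, 70, 55, 47.5 | −30%, −21.4%, −13.6% | −30%, −45%, −52.5% | none by month 3 |

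Varying the half-time for P = 40:

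- h = 0.5 month: 100, 70, 62.5, 60.6. Last change −3.0%.
- h = 2 months: 100, 88.3, 80, 74.1. Last change −7.3%.

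Both first trigger at month 3. Measured from baseline, none of the six paths triggers at any visit.

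**6. How long a one-month change can be seen.** On the text's schedule, only through month 3, because draws are then quarterly. On Table 2's, until steady state, which has no date and is not defined. At steady state the month-to-month change is near zero, so under visit-to-visit comparison, reaching it would itself tend to meet the trigger.

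**The case against.** The best defence is that the sentence was written as one early check of response to the starting dose. Two features support it. The milligram figure is a doubling only from 35 mg weekly, and the follow-on sentence speaks of values that remain high, so the authors probably had patients with persistently high BSAP in mind. Nothing says that the test is repeated at every visit. The lower-limit stop has no exception, so it still applies after any increase, and Table 2 continues BSAP draws to two years. The post-hold case needs a narrow run of visits under the text's schedule. The study team meets weekly on protocol compliance, which should catch some misreadings.

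Most of this stands, and it limits the point. It does not remove it: the trigger as written has no level condition, restarted patients are not mentioned, and the stop acts only after BSAP has fallen again. A procedures figure is attached to the protocol but is not in the text available here. It may be clearer, but the paragraph would still contradict itself.

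A reader might infer that the protocol doubles the dose of responders at plateau. The documents do not support that as a flat statement: it needs both visit-to-visit comparison and repeated testing, and neither is stated.

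**Conclusion.** The point holds as an internal contradiction together with an under-specified rule.

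- **Firm:** for a patient restarted on 35 mg every other week, the sentence gives two different doses, 35 mg and 70 mg a week. Whether it covers such a patient, what BSAP is compared with and how often the test is made are all unstated. The text and Table 2 differ on how long monthly draws last.
- **Conditional:** a responder near plateau can meet the trigger if each visit is compared with the previous one and the test is repeated. The size of that effect rests on assumed paths. The 76% and 83% figures assume assay error only, at the stated upper limits.

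Other stronger readings are tempting. One is that an over-suppressed patient goes to four times the restart dose. That is one of two literal readings, the other being twofold. Another is that patients would be exposed to femoral fracture risk: the protocol ties those fractures to more than five years of use, and study treatment totals two. A third is that the one-year BMD effect would not describe a reproducible regimen. That is too strong for an ambiguity confined mainly to the monthly-draw period of a titrated arm. It remains worth correcting, because a literal reading can work against the paragraph's own safety aim.

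**What to change.** The sponsor should reconcile the restart sentence, the increase sentence and the alendronate block of Table 2 so that together they state:

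- one comparison value for the 8% test;
- the visit or visits at which the test is made, and how many times;
- whether it applies to patients restarted after a hold;
- a dose instruction in which the word and the milligram figure agree for every patient it covers;
- one duration for monthly BSAP draws, the same in the text and in Table 2.

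The result should be checked against the paragraph's aim of preventing over-suppression. Which comparison, rule or dose is right is for the sponsor to decide.

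The cost is one or two sentences in an amendment, with Table 2 aligned. No new data are needed.
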